9.5 Study Size

242 patients with confirmed diagnosis of Highly Active Relapsing-Remitting Multiple Sclerosis (RRMS) will be enrolled in the participating countries.

CCI	
	7

9.6 Data Management

The main purpose of the (e)CRF is to obtain data required by the non-interventional study protocol in a complete, accurate, legible and timely manner. The data in the (e)CRF should be consistent with the relevant source documents.

The Investigator or designee is responsible for ensuring that the data collected in the course of this study is accurate and documented appropriately on all applicable forms. Data will then be processed, evaluated, and stored in anonymous form in accordance with applicable data protection regulations. The Investigator must ensure that the (e)CRFs and any other associated documents forwarded to Sponsor or its designated organization contain no mention of any subject names.

The data will be entered into a validated database. The Sponsor/CRO or its designee will be responsible for data processing, in accordance with the Sponsor's/CRO's data management procedures. Database lock will occur once quality control and quality assurance procedures (including SAE/SADR reconciliation) and coding activities have been completed. PDF files of the (e)CRFs will be provided to the investigators at the completion of the study.

9.7 Data Analysis

Statistical programming and analyses will be performed using SAS 9.4 (or higher). Detailed methodology for summary and statistical analyses of data collected in this study will be documented in a statistical analysis plan (SAP), which will be finalized prior to database lock and will be included in the clinical study report for this protocol. The final SAP will take into account any amendment to the protocol.

All analyses will be performed on patients who received at least one dose of Cladribine tablets following enrollment in the study.

9.7.1 Analysis Sets

Full Analysis Set

The Full Analysis Set (FAS) is defined as all the patients who provided informed consent and who received at least one dose of Cladribine. A subgroup analysis will be conducted on FAS, as described in Section 9.7.3.

9.7.2 Derived and Transformed Data

Missing information will be captured for quantitative as well as qualitative variables by the category "Missing" in the summary statistics. If there are no missing values this will be indicated by "0" unless otherwise specified. Due to the longitutinal nature of the data and the lengthy follow-up period, it is possible that missing outcome data will be present. Patterns and degrees of missingness will be summarized. In general no impution of missing data will be done.

9.7.3 Statistical Methods

All endpoints will be presented by descriptive statistics for baseline, 12-months, and End of Study assessments. Assessments done at 6-months and 18-months will be presented similarly. Quantitative (continuous) variables will be summarized with the use of descriptive statistical measures [mean value, standard deviation (SD), median, min-max, Q1-Q3]. Qualitative (categorical) variables will be displayed as frequencies and percentages (N, %).

The normality of distributions will be examined using the Shapiro-Wilk test in order to determine whether or not to use parametric methods for analysis.

Primary Endpoint: Pre- and post- baseline ARR will be compared by ANOVA or Wilcoxon signed-rank test if data is not normally distributed. The 95% Confidence Interval (CI) for the difference will be presented.

If appropriate, sensitivity analyses will be done to determine the impact of confounding factors or to describe the outcome for special subject groups fulfilling predefined criteria. Details will be described in the SAP.

For **Secondary and exploratory endpoints** the following calculations and comparisons will be performed:

- Pre- and post- baseline ARR (1 year) will be compared by ANOVA or Wilcoxon signed-rank test if data is not normally distributed. The 95% Confidence Interval (CI) for the difference will be presented.
- For all other secondary endpoints, 95% CI will be calculated for the result at each timepoint and for the differences whenever applicable, using appropriate methods.

In the analysis of 6-month disability progression/improvement EDSS, T25FW and 9-HPT values must be obtained at sequential time points, separated by 6-month intervals. As T25FW and 9-HPT are optional and will be performed if done as per routine practice, missing values may occur and could lead to bias in their analysis. Methods to handle this bias issue will be described in detail in SAP.

A subgroup analysis will be conducted on effectiveness endpoints (ARR at 1 and 2 years, percentage of patients with 6-month disability progression and improvement), with 5 groups defined according to the pre-baseline DMD treatment (IFN- B 1a / IFN- B 1 B / Glatiramer Acetate, Teriflunomide, DMF).

CCI			

9.7.4 Sequence of Analyses

Main analysis will be performed once all the patients completed the study with the purpose of evaluating all endpoints and database is locked. Two descriptive interim analyses will be performed, respectively when 30% and 60% of the patients have completed the 12-month follow-up visit, to also observe pre-baseline ARR and the variances adherence with sample size assumptions. An alpha adjustment for the multiplicity of the analysis will be introduced if the interim analysis will lead to change in sample size strategy. The Interim Analyses will be based on a subset of main analysis outputs and the list will be detailed in the SAP.

9.8 Quality Control

Quality control activities will include verification of data and ensure the data collected in (e)CRF is accurate, valid and in accordance with the protocol.

9.9 Limitations of the Research Methods

This study is open label and observational, and therefore has inherent limitations in terms of susceptibility to bias, confounding and restricting the ability to define causality. There is limited control over patient assessment as patient monitoring and diagnostics are per standard of care; no additional clinical monitoring is generally conducted. Patient specific methodological challenges such as potential biases from patient selection, loss of patients through study attrition, and overall patient recall are also other limitations. However, observational study strengths include that they reflect daily clinical practice more closely than randomized controlled trials, both in terms of the heterogeneous patient populations that are included, and the medical interventions that they receive. Real-life observational data is essential to assess and improve clinical practice worldwide and complement randomized controlled trials by providing clinically-relevant, real-world data and provide considerable health economic information.

9.10 Other Aspects

9.10.1 Independent Ethics Committee or Institutional Review Board

Prior to commencement of the study at a given site, the protocol will be submitted together with its associated documents (informed consent form, PROs, etc.) to the responsible Independent Ethics Committee (IEC) for its favorable opinion/approval. The written favorable opinion/approval of the IEC will be filed by the Investigator and a copy will be sent to the Sponsor.

The study must not start at a site before the Sponsor has obtained written confirmation of favorable opinion/approval from the concerned IEC. The IEC will be asked to provide documentation of the date of the meeting at which the favorable opinion/approval was given, and of the members and voting members present at the meeting. Written evidence of favorable opinion/approval that clearly identifies the study, the protocol version, and the Subject Information and Consent Form version reviewed should be provided. Where possible, copies of the meeting minutes should be obtained.

Amendments to the protocol will also be submitted to the concerned IEC, before implementation in case of substantial changes.

9.10.2 Monitoring

Risk based monitoring will be performed for this study. Risk based monitoring is the process of ensuring the quality of clinical studies by identifying, assessing, monitoring and mitigating the risks that could affect the quality or safety of a study. It can facilitate efficient trial delivery without compromising patient safety or data quality. A Sponsor or an appointed CRO will identify critical data and processes, performs a risk assessment and then develops a monitoring plan that focuses on the important and likely risks to critical data and processes.

A Sponsor or an appointed CRO Monitor will mainly perform 'remote' monitoring calls at regular intervals.

'On site' visits may be performed, if required, at any time during the study. For hospitals where potential quality risks are identified, on-site visits can verify that the study is being carried out according to the protocol.

Monitoring on-site visits will involve checking of CRFs against original patient records and identification of any questions or problems related to study conduct or data collection. Investigators must therefore ensure that the Monitor has access to relevant documents during monitoring visits, and that they and/or relevant site staff members are available to discuss any issues that may arise.

The study Monitor will send monitoring reports to the Sponsor.

9.10.3 Health Authorities

The protocol will be notified to the National Health Authorities register in accordance with the regulations of each country for non-interventional studies.

9.10.4 Quality Assurance

In compliance with regulatory requirements, the Sponsor, a third party on behalf of the Sponsor, regulatory agencies, or IECs may conduct quality assurance audits/inspections at any time during or following a study. The Investigator must agree to allow auditors/inspectors direct access to all study-related documents, including source documents, and must agree to allocate his or her time and the time of his or her study staff to the auditors/inspectors in order to discuss findings and issues.

The protocol, each step of the data capture procedure, and the handling of the data, as well as the study report, may be subject to independent Clinical Quality Assurance. Audits may be conducted at any time during or after the study to ensure the validity and integrity of the study data.

9.10.5 Archiving

The archive should be maintained for the period specified by local regulations, where applicable. All original subject files (medical records) must be stored at the site (hospital, research institute, or practice) for the longest possible time permitted by the applicable regulations. In the absence of applicable regulations, the archive should be maintained for at least 5 years after the final study report or the first publication of study results, whichever comes later. In any case, the Investigator should ensure that no destruction of medical records is performed without the written approval of the Sponsor.

10 Protection of Patients

10.1 Subject Information and Informed Consent

An unconditional prerequisite for a subject's participation in the study is his/her written informed consent. The subject's written informed consent to participate in the study must be given before any study-related activities are carried out.

Adequate information must therefore be given to the subject by the Investigator before informed consent is obtained (a person designated by the Investigator may give the information, if permitted by local regulations). A subject information sheet in the local language will be provided by the Sponsor for the purpose of obtaining informed consent. In addition to providing this written information to a potential subject, the Investigator or his/her designee will inform the subject verbally of all pertinent aspects of the study (the language used in doing so must be chosen so that the information can be fully and readily understood by laypersons). Depending on national regulations, a person other than the Investigator may inform the subject and sign the Informed Consent Form.

The Informed Consent Form must be signed and personally dated by the subject and the Investigator. The signed and dated declaration of informed consent will remain at the Investigator's site, and must be safely archived by the Investigator. A copy of the signed and dated information and consent form should be provided to the subject prior to participation.

Whenever important new information becomes available that may be relevant to the subject's consent, the written subject information sheet and any other written information provided to patients will be revised by the Sponsor and be submitted again to the IEC/IRB for review and favorable opinion. The agreed, revised information will be forwarded to each subject in the study. The Investigator will explain the changes to the previous version.

10.2 Subject Identification and Privacy

A unique patient number will be assigned to each subject at inclusion. This number will serve as the subject's identifier in the study as well in the study database.

The Investigator must ensure that the patients' anonymity is maintained. On the CRFs or other documents submitted to the Sponsor, patients should not be identified by their names, but by their

assigned identification numbers. If subject names are included on copies of documents submitted to the Sponsor, the names (except for initials) must be obliterated and the assigned subject numbers added to the documents.

The Investigator should keep a separate log of patients' identification numbers, names, addresses, telephone numbers and hospital numbers (if applicable). Documents not for submission to the Sponsor, such as signed Informed Consent Forms, should be maintained in strict confidence by the Investigator.

Only authorized persons will have access to identifiable personal details, if required for data verification. The subject's original medical data that are reviewed at the site during source data verification by the Monitor, audits, and Health Authority inspections will be kept strictly confidential. The Investigator agrees to provide direct access to these documents to the Sponsor and to Health Authority representatives. The Investigator is responsible for retrieving information from personal medical records.

Data protection and privacy regulations will be observed in capturing, forwarding, processing, and storing subject data. Patients will be informed accordingly, and will be requested to give their consent on data handling procedures in accordance with national regulations.

11 Management and Reporting of Adverse Events

11.1 Adverse Events

Adverse Event (AE)

An AE is any untoward medical occurrence in a patient or clinical study subject administered a pharmaceutical product and which does not necessarily have a causal relationship with this treatment. An AE can therefore be any unfavorable and unintended sign (including an abnormal laboratory finding), symptom, or disease temporally associated with the use of a medicinal product, whether or not considered related to the medicinal product.

Adverse Drug Reaction (ADR)

An ADR is a response to a medicinal product which is noxious and unintended.

Response in this context means that a causal relationship between a medicinal product and an AE is at least a reasonable possibility.

ADRs may arise from use of the product within or outside the terms of the marketing authorization or from occupational exposure. Conditions of use outside the marketing authorization include off-label use, overdose, misuse, abuse and medication errors.

Reports of Special Situations: Pregnancy, overdose, off-label use, misuse, medication error or occupational exposure, lack of therapeutic effectiveness and others

CONFIDENTIAL INFORMATION

- Use of a medicinal product during pregnancy or breastfeeding: reports where embryo, fetus or child may have been exposed to medicinal products (either through maternal exposure or transmission of a medicinal product via semen following paternal exposure)
- Reports of overdose, abuse, off-label use, misuse, medication error or occupational exposure
- Lack of therapeutic effectiveness
- Prescription error/dispensing error, e.g. due to confusion of invented names of the medicinal products
- Drug interaction
- Suspected transmission of an infectious agent via a medicinal product
- Product complaints, including falsified product or counterfeit

Reports of special situation with no associated adverse reaction will not be submitted to the authorities as ICSRs. They will be collected and considered in the study report or any interim reports, as applicable.

Serious Adverse Event (SAE)/Serious Adverse Drug Reaction (SADR)

An SAE/SADR is any AE/ADR as defined above, which also fulfills at least one of the seriousness criteria below:

- Results in death
- Is life-threatening¹⁾
- · Requires in-patient hospitalization or prolongation of existing hospitalization
- Results in persistent or significant disability/incapacity
- Is a congenital anomaly/birth defect
- Is otherwise considered as medically important²⁾
- 1) Life-threatening in this context refers to a reaction in which the patient was at risk of death at the time of the reaction; it does not refer to a reaction that hypothetically might have caused death if more severe.
- 2) Medical and scientific judgement should be exercised in deciding whether other situations should be considered as serious reactions, such as important medical events that might not be immediately life threatening or result in death or hospitalization but might jeopardise the patient or might require an intervention to prevent one of the other outcomes listed above. Such important medical events should be considered as serious.

Examples of such events are intensive treatment in an emergency room or at home for allergic bronchospasm, blood dyscrasias or convulsions that do not result in hospitalization or development of dependency or abuse. As a guidance, the important medical event (IME) terms list is intended to be used for assessment of suspected adverse reactions (see EMA/207865/2017).

Any suspected transmission via a medicinal product of an infectious agent is also considered a serious adverse reaction.

Adverse Events of Special Interest (AESI)

An AESI is an AE of scientific and medical concern specific to the sponsor's product or program, for which ongoing monitoring and rapid communication by the Investigator to the sponsor can be

appropriate. AESIs for monitoring should then be collected following the procedure for an SAE described in Section 11.4.

The study-specific data will be registered for each of the following events and the known related risk factors:

For complete and accurate information, the data collected on these pre-defined events will include as much detail as possible to corroborate diagnosis, including but not limited to histopathologic results, and relevant laboratory and imaging results.

Malignancy: Any occurrence of malignant neoplasms during the study period. These will be classified overall and by type. Malignancies will include all physician-diagnosed and pathologically confirmed solid tumours (including non-melanoma skin cancer) and lymphoproliferative/haematopoietic neoplastic diseases. Benign tumours will not be collected.

Severe and/or serious infections: The above mentioned 4 categories will follow as: Any occurrence during the study period, regardless of the causative agent and the duration of infection, will be recorded. All of the following will be considered:

- · Bacterial, viral, fungal, parasitic and protozoal infections
- Severe and/or serious infections will be defined by their management or their outcome: all
 infections that result in death or hospitalisation or require the use of intravenous treatment
 (e.g. antibiotics)
- Opportunistic infections are defined as an invasive infection caused by microorganisms that
 are normally non-pathogenic or rarely pathogenic in individuals with normal immune
 function or cause an infection of a type or severity not seen in the normal host; opportunistic
 infections exclude herpetic infection
- Herpes zoster (not considered an opportunistic infection). Only severe and/or serious herpes zoster will be collected.

The duration of infections will be the difference between start date and recovery date as reported by the treating physician.

Patients may contribute more than I episode to this analysis if, after resolution as defined, another infection occurs.

Severe lymphopenia: Any occurrence of severe (or worse) lymphopenia during the study period, classified as Grade ≥ 3. As per the Common Terminology Criteria for Adverse Events (CTCAE) (v4.03: June 14, 2010) from the National Institutes of Health, the grades of lymphopenia are defined based on laboratory test results that indicate a decrease in number of lymphocytes in a blood sample:

- Grade 3 (severe lymphopenia): <500 200/mm³; <0.5 0.2 x10⁹ /L
- Grade 4 (serious lymphopenia): <200/mm³; <0.2 x 10⁹ /L

Duration of severe lymphopenia: It is defined as the interval from the finding of severe lymphopenia until resolution, which is the achievement of a CTCAE Grade I [ranging from the

lower limit of normal (LLN) to 800/mm³] or normalization (above LLN i.e. normal lymphocyte count or CTCAE Grade 0). Patients may contribute more than 1 episode to this analysis if, after resolution as defined, severe lymphopenia occurs again. The frequency of lymphocyte counts in patients with severe lymphopenia will be described with special emphasis on the number and timing of lymphocyte counts in relation to Cladribine tablets dosing and during episodes of severe lymphopenia.

Events not to be considered as Adverse Events

Medical conditions present at study start, that do not worsen in severity or frequency during the study are defined as Baseline Medical Conditions and are NOT to be considered AEs.

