9.3 Variables

- Demographic data: Gender, age, race (if allowed as per local regulation)
- Other Baseline Assessments: Weight
- Medical history, including MS, malignancies, severe and opportunistic infections
- MS-Medication history: DMD, immunosuppressive/immunomodulatory agents (other than DMD, such as corticosteroid treatment)
- Therapy with Cladribine Tablets [date of administration and number of tablets taken versus prescribed dose (treatment adherence)]
- Reason for switching from first line DMD to Cladribine Tablets
- Participation in a Cladribine Patient Support Program
- Course of disease
 - o Relapses
 - o MRI data
 - T2, T1 Gd+ and CUA lesion counts
 - o EDSS Score
 - o T25FW (time in seconds, optional)
 - o 9-HPT (time in seconds, optional)
- TSQM-v1.4 VAS score
- MSIS-29 score

- · EQ-5D-3L score
- Safety (Serious Adverse Events (SAEs), Adverse Events of Special Interest (AESI) and Adverse Drug Reactions (ADRs))

Derived and transformed data needed for the analysis are described in Section 9.7.2.

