11.2 Severity of Adverse Events

Investigators should assess the severity/intensity of any AE as follows:

Mild: The subject is aware of the event or symptom, but the event or symptom is easily

tolerated.

Moderate: The subject experiences sufficient discomfort to interfere with or reduce his or

her usual level of activity.

Severe: Significant impairment of functioning: the subject is unable to carry out usual

activities.

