## 7 Changes to the Planned Analyses in the Clinical Study Protocol

There are no changes to the analyses planned per protocol.

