#### 15.1.1 All Adverse Events

The AEs will be summarized using the latest version of MedDRA PT as event category and MedDRA primary SOC body term as body system category.

Incomplete AE-related dates will be handled as specified in Section 9.8.1.

The following tables will be created

- TEAE summary table with the number and percentage of patients having:
  - o TEAE
  - TEAE of Special Interest (TEAESI)
  - TEAE leading to death
  - o TEAE leading to Cladribine dose reduction
  - o TEAE leading to Cladribine temporary discontinuation
  - o TEAE leading to Cladribine permanent discontinuation
  - TEAE leading to study termination
  - TEAE not recovered/resolved
  - Any serious TEAE:
    - TEAESI
    - Leading to death
    - Leading to Cladribine dose reduction

- Leading to Cladribine temporary discontinuation
- Leading to Cladribine permanent discontinuation
- Leading to study termination
- Not recovered/resolved
- Cladribine related TEAE:
  - TEAESI
  - Serious
  - Leading to death
  - Leading to Cladribine dose reduction
  - Leading to Cladribine temporary discontinuation
  - Leading to Cladribine permanent discontinuation
  - Leading to study termination
  - Not recovered/resolved
- Incidence of TEAE by Primary SOC and PT
- Incidence of Serious TEAE by Primary SOC and PT
- Incidence of Serious TEAE related to Cladribine by Primary SOC and PT
- Incidence of TEAE leading to Cladribine temporary discontinuation Primary SOC and PT
- Incidence of related TEAE leading to Cladribine temporary discontinuation Primary SOC and PT
- Incidence of TEAE leading to Cladribine permanent discontinuation Primary SOC and PT
- Incidence of related TEAE leading to Cladribine permanent discontinuation Primary SOC and PT
- Incidence of TEAE leading to death by Primary SOC and PT
- Incidence of related TEAE leading to death by Primary SOC and PT
- Incidence of TEAE by Primary SOC and PT and relationship to Cladribine
- Incidence of TEAE by Primary SOC and PT and severity
- Incidence of TEAESI by Primary SOC and PT and severity
- Incidence of TEAESI by Primary SOC and PT and by relationship to Cladribine

2.0

• Incidence of Serious TEAESI by Primary SOC and PT and by relationship to Cladribine

All AEs regardless of being treatment-emergent or not will be listed.

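### The protocol promises count-based results for severe lymphopenia that the SAP does not plan, and special-interest events are tabulated on a severity scale unrelated to CTCAE grade

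*Protocol*

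**What the plan says.** **Protocol 11.1.** Severe lymphopenia is an adverse event of special interest (AESI), and "the grades of lymphopenia are defined based on laboratory test results". Grade 3 is a count below 500 down to 200/mm³; Grade 4 is below 200/mm³. Three descriptive elements follow:

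- duration: "Duration of severe lymphopenia: It is defined as the interval from the finding of severe lymphopenia until resolution", where resolution means reaching CTCAE Grade 1 (800/mm³ up to the lower limit of normal) or a normal count;
- repeat episodes: "Patients may contribute more than 1 episode to this analysis if, after resolution as defined, severe lymphopenia occurs again";
- testing: "The frequency of lymphocyte counts in patients with severe lymphopenia will be described with special emphasis on the number and timing of lymphocyte counts". The timing meant is that relative to dosing and within episodes.

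**Protocol 11.2** gives one severity scale for all adverse events, based on tolerability and function. Its lowest level begins "The subject is aware of the event or symptom, but the event or symptom is easily" (tolerated).

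**Protocol 9.3** lists, for safety, only "Safety (Serious Adverse Events (SAEs), Adverse Events of Special Interest (AESI) and Adverse Drug Reactions (ADRs".

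**SAP 15.1.1** plans "Incidence of TEAESI by Primary SOC and PT and severity", with further AESI tables by relationship to cladribine. SAP 15.1 counts each participant once per system organ class or preferred term. **SAP 7** states: "There are no changes to the analyses planned per protocol".

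**The concern.** The protocol treats severe lymphopenia as a laboratory event with a grade, a time course and a testing pattern. The SAP treats it as one more adverse-event term. Safety at two years is a secondary objective, and protocol 7.2 names lymphopenia as the most commonly reported adverse event in the pivotal placebo-controlled trial. If the plan is followed as written, the report will show how many patients had a severe lymphopenia term and how the investigator rated its functional impact. No planned table will show how deep the lymphopenia was, how long it lasted by the protocol's own definition, whether it recurred, or how closely those patients were monitored.

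**Working it through.** No formula applies; the check sets the protocol's lymphopenia elements against the data listed for collection and the outputs planned.

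**1. Are the inputs listed for collection?** Neither the legible rows of Table 1 nor the visit lists in protocol 9.2.4 contain a lymphocyte or haematology item. A few entries there are blacked out, but 9.3 has no such gap and no laboratory variable. Non-interventional status does not explain this: MRI is also done only in routine care, yet it is listed for collection when available. The one route in the text is 11.1, which asks for as much supporting detail as possible on each AESI, including relevant laboratory results, without itemising counts or their dates. Protocol 9.2.2 ties the Year 2 course to lymphocyte recovery, so routine counts probably exist in the records; that is an inference.

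**2. Are the outputs planned?**

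| Element in protocol 11.1 | Planned SAP output |
|---|---|
| Grade 3 versus Grade 4 | None; AESIs are split by severity, not CTCAE grade |
| Duration to Grade 1 or normal | None; SAP 9.3 has only a generic stop-minus-start rule |
| Repeat episodes | None; SAP 15.1 counts a patient once per preferred term |
| Number and timing of counts | None |

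So none of the four elements has an output. The SAP text available does not mention lymphopenia, lymphocytes or CTCAE, and the interim list in Appendix 18.2 adds only a table of AESIs by class and term.

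**3. Would adverse-event dates stand in for the defined duration?** Only by chance. Severe lymphopenia starts below 500/mm³ but resolves, under 11.1, only at 800/mm³ or above. Between those limits the patient is no longer Grade 3 but the episode is still open. A site that closes the event once the count passes 500 records a shorter episode than one that waits for 800. The episode count changes too: a course of 450, 600, 450/mm³ is one episode under 11.1 but two if the event is closed at 600.

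**4. Which scale fills the severity column?** Protocol 11.4 has the investigator record severity with the word grading in brackets, but names no scale. The SAP does not define severity. Protocol 11.2 is therefore the only scale available, and it applies to any adverse event. Grade 3 and Grade 4 differ by cell count, which that scale does not use, so it cannot separate them. An event that 11.1 calls severe by count can be rated below severe by function.

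**The case against.** Several counter-arguments have weight.

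- **Cases are not lost.** Grade 3 or higher is the entry criterion for this AESI, so a reported case enters the tables whatever severity is ticked. This stands, and it limits the damage to the severity column and the missing summaries.
- **Mild is not the inevitable label.** A reader might infer that every symptom-free Grade 3 or 4 case will be reported as mild. The documents do not support that. The lowest level in 11.2 presupposes awareness of the event, so a silent laboratory finding fits no level cleanly, and 11.1 itself calls Grade 3 severe. The text establishes ambiguity and possible conflict, not systematic misgrading.
- **Counts may be captured.** The promised description covers only patients with severe lymphopenia, who are the patients with an AESI report. Protocol 11.5 names an AESI form that is not among the documents and may hold dated counts. This is fair, but nothing in the text requires it.
- **A duration can be derived.** Onset and resolution dates are collected and all adverse events are listed. That gives a crude duration, with the limits shown above, and no table is planned for it.
- **SAP section 7 may be read narrowly.** SAP section 4 says the SAP covers the analyses in protocol 9.7, while the lymphopenia text sits in 11.1. On that reading the no-changes statement is not strictly false. The promised description still has no home in either analysis section.

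**Conclusion.** There is a real gap between protocol 11.1 and the SAP. Four count-based elements of a special-interest event have no planned output, the counts behind them are not a listed variable, and the severity table uses a scale that cannot reproduce the Grade 3/4 distinction and can contradict the event's definition. This should be corrected. It affects the safety report, not the primary endpoint.

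A reader might go further and infer that the reported incidence of severe lymphopenia is too low by a calculable amount, because SAP section 9 by default divides by the whole analysis set, including any patients never tested. The documents give neither the share tested nor the true incidence, so no size can be stated, and they promise no incidence among tested patients. It is also not an error that a non-interventional study schedules no laboratory tests. The fault is promising a description of routine counts without listing them for collection or planning its output.

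The conclusion assumes that the AESI form and eCRF, which were not available, do not already itemise dated counts and CTCAE grade. If they do, the collection gap closes and the SAP gap remains.

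**What to change.** **Collection.** For each reported severe lymphopenia AESI, record the dates and values of lymphocyte counts obtained in routine care, if available, as is done for MRI, and add the item to protocol 9.3. Record CTCAE grade in its own field beside the 11.2 severity rather than replacing it, so that 11.2 still applies to every adverse event.

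**Analysis.** Add SAP outputs for:

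- lymphopenia by CTCAE grade;
- number of episodes per patient, as an exception to the once-per-term rule;
- duration by the 11.1 definition;
- number and timing of counts relative to dosing and within episodes. Dosing dates are already collected.

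**Alternative.** If the sponsor does not want these data, remove the promise from 11.1 and declare the change in SAP section 7.

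**Optional.** Report how many patients in the full analysis set had at least one count after first dose, as context for the incidence. This needs a simple field for all patients, since counts recorded only for reported cases cannot supply it.

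**Cost.** Modest extra transcription at sites and a few tables. No added testing and no change to patient management.
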